This is a single-center, prospective, ‘open-label,’ investigator-initiated pilot study evaluating the role of continuous glucose monitor (CGM) use either alone or with remote monitoring capabilities that enable subjects to share CGM data with family and friends (whom we will call “followers” in this protocol) among women with T1DM associated with pregnancy. We hypothesize that CGM use will decrease percentage of glucose values below the target range, decrease frequency of severe hypoglycemic episodes, and increase post-prandial glucose values into the target range, with a possible reduction in A1C compared to not using CGM during pregnancy. We hypothesize that the use of remote technology (**Share™ technology**) with subject’s designated follower will decrease hypoglycemia fear and the frequency of severe hypoglycemic episodes compared to CGM use alone in pregnancy or not using CGM use in pregnancy. This study aims to improve maternal glucose management among women with T1DM with a hope to also improve health outcomes during pregnancy.

The study will enroll up to 40 patients from the Barbara Davis Center for Childhood Diabetes (BDC) Adult clinic over the age of 18 years who are pregnant (13 weeks gestation or less) or plan to become pregnant within the following 6 months. The study will also attempt to enroll up to 40 followers (one per pregnant subject) who are family members or friends of the pregnant subjects and over the age of 18 years. All subjects meeting these criteria will be invited to sign informed consent and participate in the study. All pregnant subjects will be stratified into one of three groups: (1) CGM use alone, (2) CGM use with Share™, (3) no CGM use. CGM use will be offered to all subjects, but individuals who do not want to wear a CGM will be stratified to Group 3. Stratification for Groups 1 and 2 will depend on the following: subjects and followers who have iPhones, iPads, and/or iPod touches will be placed into Group 2 which requires one of these devices to function, while all others will be placed in Group 1. All subjects will be followed for study visits with similar frequency during the pregnancy, and subjects in Groups 1 and 2 will wear the Dexcom G4 Platinum® CGM system from the first pregnancy visit until delivery. All subjects in Group 2 will also use the Share™ technology from the first pregnancy visit until delivery.

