CGM data will be analyzed for mean blood glucose values, time spent in hyperglycemic (>240, >300mg/dl) and hypoglycemic (<50, <70, <80 mg/dl) ranges and various indices of glycemic variability. Laboratory analysis for A1C will be performed at baseline, monthly thereafter during the pregnancy, and post-partum. Routine blood tests will be performed in all subjects in each trimester (see Table 1).

Primary outcomes will be:

- 1) Glucose variability as measured by glucose excursions from self-monitoring blood glucose (SMBG) data through log books and downloads as well as CGM downloads and various indices [J-index, mean amplitude of glycemic excursion (MAGE), high blood glucose index (HBGI), low blood glucose index (LBGI)] from CGM downloads.
- 2) Changes detected by the hypoglycemia fear questionnaire.

Secondary outcomes will be:

- 1) How CGM alone and CGM with Share™ usage affect A1C compared to no CGM use,
- 2) Progression of diabetes complications (retinopathy, nephropathy),
- 3) Maternal and fetal outcomes (eclampsia/pre-eclampsia, live birth rates, birth weight, neonatal hypoglycemia, and other similar measures).

Introduction:

Among the US population, 29.1 million people (9.3%) have diabetes (1). Pre-existing diabetes has to be managed very carefully throughout pregnancy to optimize maternal and fetal outcomes (2). Among women

with T1DM who are pregnant, the tools that we have to regulate maternal glucose control include multiple daily injections (MDI), continuous subcutaneous insulin infusion therapy (CSII) also known as insulin pump therapy, and for high-risk individuals continuous glucose monitoring (CGM) (2). CGM use in pregnancy has been shown to be safe, to reduce the frequency of severe hypoglycemia, and to improve A1C values (3-6). Sensor-augmented pump therapy with CGM use continuously was shown to lower A1C more than intermittent use in pregnant women with T1DM (7). However, few studies have measured changes in glucose variability that occur with CGM use during pregnancy and no studies have evaluated how tools that allow family and friends (followers) to access glucose trends affect outcomes during pregnancy.

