The goal of this prospective, non-randomized, pilot quality improvement study is to evaluate how CGM usage with and without remote monitoring capabilities affects glucose variability, A1C control, and patient-related outcomes compared to non-CGM use in pregnancy among women with T1DM. This study may lead to further investigations about the role of mobile phones and handheld devices (such as iPod touch) for T1DM self-care in pregnancy.

The Barbara Davis Center (BDC) Adult Clinic follows ~3,000 patients with T1DM. [name], MPH is this study's Principal Investigator and the director of the Pregnancy and Women's Health Clinic at the BDC, which includes an extensive multidisciplinary team (physician's assistant, nurse practitioner, registered nurses, certified diabetes educators, registered dieticians, and a social worker). The BDC Pregnancy and Women's Health Clinic has all the necessary resources to perform such a trial. Moreover, the investigators have extensive experience conducting clinical trials, including trials during pregnancy.

Primary Objectives:

The primary objectives of this pilot study are to improve maternal glucose management, to assess the role of CGM usage either alone or with remote monitoring capabilities (Share™) and changes detected by the hypoglycemia fear questionnaire among women with T1DM associated with pregnancy.

Secondary objectives:

1. Assessment of remote monitoring capabilities of followers (Share™ usage) that lead to interventions for hypoglycemia and hyperglycemia that affect subjects wearing CGM.
2. Reduction in A1C from baseline to 3 months with maintained control at 6 and 9 months.
3. Assess progression or stability of diabetes complications (retinopathy, nephropathy).
4. Assess effects of CGM usage on maternal and fetal health outcomes (eclampsia/pre-eclampsia, live birth rates, birth weight, neonatal hypoglycemia, and other similar measures).

Research Design:

What do we intend to do?

We intend to execute a single-center, prospective, non-randomized, 'open-label,' investigator initiated pilot study evaluating the effect of CGM usage with or without remote monitoring capabilities on women with T1D throughout pregnancy and compare outcomes to women who do not use a CGM during pregnancy. We also intend to ask a main follower for each woman about his/her knowledge of extreme glucose values among subjects and interventions on a subject's behalf. See Figure 1 for study design.

How are we going to do the work?

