During this visit, pregnant subjects will receive a physical exam, vitals, medical history, demographics, and concomitant medications. Laboratory tests will be performed to assess for A1C. SMBG values will be downloaded. If applicable CGM units and insulin pumps will be downloaded.

Stratification, Visit 2 (Week 1):

Subjects enrolled in the study from pre-conception will be asked to come to clinic as soon as a home pregnancy test or serum blood test confirms pregnancy, during which time routine clinical care will be provided and subjects will be stratified to 1 of 3 study arms based on subject characteristics. Subjects who did not have a pre-conception counseling visit who come to clinic for routine clinical care before 13 weeks of gestation will combine Visit 1 (screening) with Visit 2 (stratification with CGM start). A urine pregnancy test will be administered to confirm pregnancy. Per routine clinical care, we will screen for diabetic neuropathy on physical exam, thyroid disease (TSH blood draw), and kidney disease (24-hour urine protein with creatinine). These tests will be repeated once each trimester. Also per routine clinical care, women will be asked to get a dilated retinal eye exam each trimester and to provide the BDC with a copy of the provider's report of each exam.

Women stratified to Groups 1 and 2 who own a Dexcom G4 or G5 Platinum CGM® will be given 4 sensors. Women stratified to Groups 1 and 2 who do not own a Dexcom G4 or G5 Platinum CGM® will be given Dexcom G4 CGM units, transmitters, and 4 sensors. They will also receive training in the insertion of sensors and CGM use. A Dexcom G4 Platinum® CGM sensor will be inserted that day and will be worn in 7 day periods throughout the study. Although subjects will be asked to wear the device 7 days/week, satisfactory data capture rate is regarded as 5 days of successful CGM readings. The CGM data will be unblinded (real-time use) such that subjects will be able to view glucose values and trends, as well as receive alerts for low and high sensor glucose values. Women will be asked to check SMBG at least 7 times daily (fasting, before meals, 2 hours after a meals, and at bedtime) for the duration of the study.

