There will also be a control arm of pregnant patients at the BDC identified through a retrospective chart review who were pregnant around the time of study enrollment or before and who did not use a CGM device throughout their pregnancies. The retrospective chart review will collect data on a subject's medical history, diabetes complications, medications, vital signs, height/weight, A1C, insulin doses, glucose meter downloads, insulin pump downloads (if applicable), and CGM downloads (if applicable) for the most immediate pre-conception visit, all pregnancy visits, and the post-partum visit. Subjects identified through the retrospective chart review will not have filled out any of our questionnaires (baseline, hypoglycemic fear, and postpartum questionnaires), nor will they have had followers who filled out questionnaires. They will not be asked to fill out these questionnaires.

Inclusion Criteria:

Subjects that meet the following criteria will be considered for admission to the study:

1. Signed informed consent before any study-related activities
2. Female aged 18 years and older with T1D duration >1 year
3. Pregnancy with confirmation of gestational age 13 weeks or less
4. Willingness to routinely practice at least 3-7 blood glucose measurements per day
5. Using MDI or CSII therapy
6. Any A1C level
7. Ability and willingness to adhere to the protocol including scheduled study visits for the duration of the pregnancy
8. Able to speak, read, and write English

Exclusion Criteria:

Subjects will be excluded from the study if any of the following apply:

1. Unwilling to sign informed consent and participate in the study
2. Female age 17 years or younger
3. T1D duration <1 year
4. Pregnancy in gestational week 14 or higher
5. Extensive skin changes/diseases that inhibit wearing a sensor on normal skin
6. Severe known allergy to adhesives within the last 3 months
7. Any other condition, as determined by the investigator, which could make the subject unsuitable for the trial, impairs the subject's suitability for the trial, or impairs the validity of the informed consent

Risks and Justification of Procedures:

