The primary endpoints are glucose variability and changes detected by hypoglycemic fear survey. We will measure indices of glucose variability (mean glucose \pm SD, % of glucose within/above/below target ranges, J Index, High Blood Glucose Index [HBGI], Low Blood Glucose Index [LBGI], Mean Amplitude of Glycemic Excursions [MAGE], CONGA_n) throughout pregnancy using the SMBG 7-point profiles for one week taken once per trimester. Hypoglycemic fear survey results will be assessed once monthly over the pregnancy. We will compare outcomes within individuals over time and between individuals of the different study arms. We will test whether outcomes differ between women using Dexcom alone and women using Dexcom with Share™ using interaction terms, and will stratify analyses if differences by group are greater than 10 mg/dL in mean glucose levels are detected. Since SMBG logs will be taken at multiple time points over the pregnancy and since CGMs will be worn continuously for the duration of each pregnancy, linear mixed models will be used to assess changes in outcome measures (GV, time spent in target below or above target) over time in each trimester of pregnancy. We will use linear mixed models to assess changes in the hypoglycemic fear survey in each month of the pregnancy. Secondary endpoints include A1C differences among study arms. Improvement in glycemic variability parameters with a possible reduction of A1C by 0.3%, measured as the difference of the mean A1C laboratory values of the arms of the study between baseline (0-3 months, first trimester), second trimester (3-6 months), and third trimester (6 to 9 months). Mixed models account for missing data, allow for an unstructured covariance matrix for repeated measures, and account for inter-subjects correlation of measurements. Secondary outcomes will be used

in the same mixed models. Differences in frequency of low alert glucose rates, high alert glucose rates, and interventions for low or high glucose values among the followers for each study arm will be analyzed with student t-tests. A p-value < 0.05 will be considered significant, and we will perform statistical analyses with SAS software (version 9.3, SAS Institute, Cary NC).

Publication Strategy:

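### The SAP labels the whole first trimester as the A1C baseline, a window that for early entrants includes values drawn on study CGM; baseline and contrast need one definition

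*Combined protocol and SAP*

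**What the plan says.** The Statistical Analysis Plan describes the A1C effect as a possible 0.3% reduction, "measured as the difference of the mean A1C laboratory values of the arms of the study between baseline (0-3 months, first trimester", then the second trimester (months 3 to 6) and the third (months 6 to 9). Secondary outcomes go into the same linear mixed models as the primary ones, with an unstructured covariance and a 0.05 threshold.

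Other sections set the timing:

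- The synopsis has Groups 1 and 2 wearing the "CGM system from the first pregnancy visit until delivery".
- The inclusion criterion is "Pregnancy with confirmation of gestational age 13 weeks or less".
- Under Stratification, Visit 2, women enrolled before conception "will be asked to come to clinic as soon as a home pregnancy test or serum blood test confirms pregnancy". Women first seen in early pregnancy "will combine Visit 1 (screening) with Visit 2 (stratification with CGM start").
- The section on Visits 3 through 13 and Table 1 call for A1C every month, with the first follow-up visit at study week 5.
- The synopsis gives the draw schedule: "Laboratory analysis for A1C will be performed at baseline, monthly thereafter during the pregnancy, and post-partum".

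The A1C aim is worded in two ways. The synopsis lists as a secondary outcome "How CGM alone and CGM with Share™ usage affect A1C compared to no CGM use". Secondary objective 2 is "Reduction in A1C from baseline to 3 months with maintained control at 6 and 9 months".

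**The concern.** A baseline should precede the intervention. Here the intervention starts at the first pregnancy visit, which the design encourages to be early, while the window called baseline stays open to the end of month 3. Early entrants in the CGM arms therefore contribute on-CGM values to their own baseline. If those values are averaged in, part of any early benefit is subtracted from the measured change.

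The second problem is a conflict of definitions. The secondary objective looks for a fall by month 3, and the SAP treats everything up to month 3 as baseline.

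The SAP also leaves open whether the 0.3 is a difference in level or in change, and in which trimester it applies. That choice decides whether the baseline window affects the result at all. The section on the study's weaknesses says the pilot should guide a much larger trial, so an A1C estimate of unclear meaning could be carried into that trial's design.

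**Working it through.** **The plan's own figure.** The only sample-size arithmetic is 40 × (1 − 0.20) = 32 completers, which reproduces. It is not derived from the 0.3, and the plan claims no formal power, so there is no stated A1C calculation to overturn.

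**Draws inside the baseline window.** From the documents: CGM starts at entry week g, g is 13 or less, and A1C is monthly. I take draws at g, g+4, g+8 and so on, up to week 13. The entry draw counts as pre-CGM because the sensor is inserted that day. An on-CGM draw falls in the window when g + 4 ≤ 13, that is, when g ≤ 9.

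**Dilution if the window is averaged.** Assumptions (none is in the documents):

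- The true effect is 0.3 points and is complete at the later trimester.
- Onset is linear over L weeks, so the fraction reached at week t is min((t − g)/L, 1).
- Every CGM-arm woman starts CGM at entry.
- Baseline is each woman's mean of all first-trimester draws, and change is compared between arms.

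Measured effect = 0.3 × (1 − mean fraction over the window).

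| Entry week | On-CGM draws | L = 4 | L = 8 | L = 12 |
|---|---|---|---|---|
| 4–5 | 2 of 3 | 0.10 | 0.15 | 0.20 |
| 6–9 | 1 of 2 | 0.15 | 0.225 | 0.25 |
| 10–13 | 0 of 1 | 0.30 | 0.30 | 0.30 |

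For example, with L = 8 and entry at week 4 the fractions are 0, 0.5 and 1. Their mean is 0.5, so 0.15 remains.

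With entry uniform over weeks 4 to 13 (two weeks in the first row, four in each of the others):

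- L = 4: (2 × 0.10 + 4 × 0.15 + 4 × 0.30)/10 = 0.20
- L = 8: (2 × 0.15 + 4 × 0.225 + 4 × 0.30)/10 = 0.24
- L = 12: (2 × 0.20 + 4 × 0.25 + 4 × 0.30)/10 = 0.26

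**When nothing is lost.** If baseline is the entry draw alone, its fraction is 0 and 0.30 is measured. If the arms are compared on second- or third-trimester level, the baseline window does not enter.

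**The two clocks.** On the SAP's gestational clock, month 3 closes the baseline window, so a change from that baseline to month 3 has no separate endpoint. Suppose instead that the objective counts from enrolment, taking 3 months as 13 weeks. A woman enrolled at week 8 then reaches month 3 at about week 21 (8 + 13), inside the SAP's second-trimester window, and month 9 at about week 47 (8 + 39), after delivery. Either way the two sections do not match.

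**Change or adjusted estimate.** Assume the CGM arm starts 0.5 lower, there is no true effect, and the baseline-to-follow-up correlation is 0.7.

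- If the arms regress to a common mean, the follow-up gap is 0.7 × 0.5 = 0.35. The change contrast is biased by −0.35 + 0.5 = +0.15 and the adjusted contrast by 0.
- If the gap is stable, the change contrast is unbiased and the adjusted contrast is biased by −0.5 + 0.35 = −0.15.

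The two biases are equal in size and opposite in sign. The documents do not say which case holds.

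**The case against.** The strongest reply is that the phrase may only name the period in which the single entry draw falls. The synopsis schedule, with one baseline draw and monthly draws after it, fits that reading. The SAP also speaks of differences among arms, which can mean levels by trimester. On either reading there is no dilution. This stands: the bias is conditional, and a reader who infers that the A1C analysis is biased as written goes beyond the documents. What remains is that the SAP does not choose, and one available choice costs part of the effect.

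Other stronger readings are also tempting, but the documents do not support them:

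- *The synopsis schedule contradicts the SAP.* It is a blood-draw schedule, not an analysis definition. The real mismatch is with secondary objective 2.
- *The units of the 0.3% are unclear.* A difference of mean laboratory values points to percentage points. Only level versus change, and the trimester, are open.
- *Omitting a baseline covariate is an error.* Allocation is by preference and device ownership, and up to 30 Group 3 women come from chart review, so imbalance is likely. But a mixed model can carry baseline as a response, and the symmetry shown above means adjustment is not uniformly better.
- *The comparison is hopelessly underpowered.* That depends on an SD the documents do not give. For 40 controls against 30 CGM users, power for 0.3 is 0.70, 0.43 or 0.24 at an assumed SD of the analysed value of 0.5, 0.7 or 1.0. If the effect is diluted to 0.2, power is 0.38, 0.22 or 0.13.

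The dilution also overstates the loss for women already using CGM at entry, because they have no new onset inside the window.

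**Conclusion.** The point holds in a limited form. As labelled, the A1C baseline window contains one or two on-CGM values for women entering by about week 9, and none for later entrants. If those values are pooled and change is compared, an assumed 0.3-point effect is measured as about 0.20 to 0.26 on average, and as little as 0.10 for entry at weeks 4 to 5 with fast onset. Entry distribution, onset and effect size are all assumptions. With the entry draw as baseline, or with later-trimester levels compared, the loss is zero.

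The mismatch with secondary objective 2 needs no assumption: the two sections must be put on one clock. Because A1C is secondary, the reduction is described only as possible, and the pilot is unpowered, the severity is minor to moderate. No sample size changes.

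**What to change.** Amend the SAP as follows:

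1. Define baseline A1C as the last value at or before study CGM start: the Visit 1 or 2 draw, or failing that the latest pre-conception value. For Group 3, including chart-review women, and for Group 1 women on a non-Dexcom CGM (who have no study CGM start), use the last value at or before the first pregnancy visit.
2. Treat later first-trimester values as outcomes, and put secondary objective 2 and the SAP on one clock.
3. State that the 0.3 is in percentage points, that it is a between-arm difference in change from this baseline, and at which trimester it is assessed.
4. As a secondary step, report the baseline-adjusted estimate beside the change estimate. Say that the change estimate assumes a stable gap and the adjusted one regression to a common mean, that the data cannot settle which is right, and that neither removes self-selection.
5. Limit any sensitivity analysis on prior CGM use to women with the Appendix B questionnaire or chart evidence of prior use. The Control Arm section says chart-review women do not complete that questionnaire.

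The cost is wording only, since the A1C values are already collected. The downsides are some missing pre-conception values, a mix of early-pregnancy and pre-conception baselines, a baseline that is not CGM-free for existing users, and two estimates that may disagree.
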